
III. Preliminary Studies/Progress Report

Preliminary data. Our pilot study was conducted at Denver Health (DH), a safety net healthcare system and early NDPP adopter, offering the program since March 2013 per CDC-established guidelines.⁷ Bilingual lay health educators received CDC-approved training to serve as NDPP coaches. New NDPP classes began every 3-6 months in DH primary care clinics, in English and Spanish. We used CDC-established NDPP eligibility criteria (e.g., A1c 5.7-6.4).³⁷ Eligible individuals were identified from medical records and referrals and enrolled through outreach calls, without fees or financial incentives to participate. Following standard NDPP delivery to 1,065 participants through July 2016 cohorts, we found disconcerting evidence of disparities in outcomes, consistent with national data⁴ (e.g., only 27% of NHBs with ≥2 recorded weights achieved the ≥5%

weight loss goal in national data, comparable to 23% of NHBs at DH). Thus, we aimed to develop a cost-effective NDPP adaptation by adding an educational and motivational "pre-session" before enrollment. NDPPs launched in September 2016 and January 2017 were preceded by these group-based meetings. In brief, participants received education on diabetes risks and information about locally available resources to reduce risk, including the NDPP. Coaches used MI techniques to help participants identify their preferred plan of action to reduce risk, such as attending the NDPP, and guided participants in identifying barriers and possible solutions to enable participation. Seventy-five participants completed a pre-session before NDPP enrollment. Another 15 individuals (17%) attended a pre-session, but did not enroll, and no further data were collected.

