Recruitment. We will identify potential participants through referrals from healthcare providers at DH, which is known to support initial enrollment in the NDPP.²¹ Providers refer through the electronic health record (EHR) per usual practice. Since 2013 over 7,000 at-risk patients were referred by providers to the DH NDPP. If needed to meet recruitment goals, we will also identify participants from a risk registry based on EHR data, which has previously identified over 10,000 NDPP-eligible patients annually. The enrollment process after initial identification will be as follows: 1) Lifestyle Coaches pre-screen via medical record review and contact referrals by phone to verify interest, eligibility, and schedule eligible individuals for an initial screening visit (held in-person or remotely as needed), 2) consenting individuals are randomized to receive Pre-NDPP or usual care NDPP (note we will use Denver Health's e-consent process for any virtually-conducted recruitment visits), and 3) complete an initial assessment (behavioral and anthropometric assessments), 4) the Pre-NDPP group completes a pre-session 1-2 weeks before NDPP classes start, 5) both groups complete a follow up behavioral

assessment 1-2 weeks before NDPP classes start (collected in-person or remotely as needed), and 6) both groups commence yearlong NDPP classes (held in-person or remotely as needed).

We will initially enroll 500 participants, with a goal of 400 randomized participants across both groups attending ≥1 NDPP session as based on statistical power estimates (see Sample Size and Power Calculations below). From previous experience, we expect approximately 50% of referred patients to express interest in participating upon initial outreach. Then after initial assessment, we expect early attrition of approximately 20% of consenting participants. We will seek to recruit 50 individuals every 3 months, for a total of 500 participants recruited over 2.5 years (i.e., 200 participants annually). From 2013-2017, we recruited 300 NDPP participants on average each year. Thus, we expect to fully meet RCT recruitment goals. Demographic characteristics of individuals in this study are expected to approximately match characteristics of all previous NDPP participants at DH: 78.0% female, 58.2% Hispanic, 19.5% NHB, 21.0% NHW, 61.4% low-income (including a majority of low-income individuals within each racial/ethnic group), and a mean age of 48.4 (SD=12.7) years.

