Retention. We aim to have 400 randomized participants across arms attending ≥1 NDPP session. We established initial retention rates during our 2013-2017 NDPP delivery and Pre-NDPP pilot as described above and in Preliminary Data (e.g., 83% [n=75] of participants attended the NDPP after completing a pre-session). We expect similar rates of early retention following the initial assessment in this study. Note dropout does not impede our ability to test main effects of Pre-NDPP on NDPP attendance and weight loss as: 1) NDPP engagement is a main outcome of interest; 2) The primary outcome of percent weight loss from baseline to 12 months will be assessed by intent-to-treat (ITT) analysis. Imputation methods for missingness will be used as appropriate (see Analysis Plan). For generalizability, we will deliver NDPP with only customary retention methods: offering classes at clinics where participants receive their primary care (with an option to join classes remotely, as allowable by the CDC since 2018²³), facilitating transportation as needed (e.g., providing free parking and information about insurance-provided transportation benefits), offering make-up sessions as needed, and updating participant contact information often. To reduce both participant and study staff burden, make up sessions will be offered primarily as a pre-recorded audio and/or video of the Lifestyle Coach talking through the session content (without other participants present). Coaches will seek to follow up briefly (e.g., 10-15 minutes) with participants via phone to ensure comprehension and address remaining questions. To accommodate additional data collection required of participants in both arms of the trial (above and beyond routine care in the NDPP), we will provide compensation of \$25 for completing each of two 30-minute research assessments at the time of initial recruitment and immediately prior to attending the NDPP. We will also provide an additional \$25 for all participants to complete a final study visit for weight measurement at 12 months (which may be collected via an in-home, study-provided scale as needed).

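### The power-based goal of 400 counts people who attend a class, while the power calculation and primary outcome need 12-month weights, for which no completion rate is given

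*Combined protocol and SAP*

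**What the plan says.** Section IV.C, Recruitment: "We will initially enroll 500 participants, with a goal of 400 randomized participants across both groups attending ≥1 NDPP session as based on statistical power". The loss allowed for is stated just after: "Then after initial assessment, we expect early attrition of approximately 20% of consenting participants". The enrolment steps in the same section run: consent and randomisation, initial assessment, pre-session (Pre-NDPP arm only), second behavioural assessment, classes.

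Section IV.C, Retention, names the source: "We established initial retention rates during our 2013-2017 NDPP delivery and Pre-NDPP pilot as described above and in Preliminary Data". The only number it gives, as an example, is "83% [n=75] of participants attended the NDPP after completing a pre-session". It then says "We expect similar rates of early retention following the initial assessment in this study", followed by "Note dropout does not impede our ability to test main effects of Pre-NDPP on NDPP attendance and weight loss". The reasons given are that engagement is itself an outcome and that the weight outcome is analysed by intention to treat, with imputation where suitable. The same section offers every participant $25 for a 12-month weight, which may come from a home scale.

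Section III gives the denominator of the 83%. Seventy-five people completed a pre-session and enrolled. "Another 15 individuals (17%) attended a pre-session, but did not enroll, and no further data were collected".

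Section IV.A defines the primary outcome as percent weight change from baseline to 12 months, whether or not the participant took up or stayed in the NDPP. Sample size and power (IV.F) uses the same population and says that 500 allows for attrition, without giving a rate.

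**The concern.** Two things do not fit together.

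First, the goal is presented as a requirement of the power calculation, but it counts attendance at one class. The power calculation needs a 12-month weight from people in either arm, including those who never attended. A person can attend one class and give no 12-month weight, or attend none and give one. Meeting the goal therefore does not show that the primary analysis has the data that Table 2 assumes.

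Second, the number offered in support of about 20% early loss starts from a later point than the loss it supports. It is conditional on having attended a pre-session, so it leaves out anyone lost between the initial assessment and the pre-session. It cannot describe usual care, and no start rate from the 2013-2017 delivery is given.

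Precision is at stake, and possibly bias. The intervention aims to change attendance. If giving a 12-month weight is related to attendance, missing weights could differ between arms. Intention to treat keeps such people in the analysis set but does not supply their weights.

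**Working it through.** **Reproducing the plan's figures.**
- Allowance (IV.C, Recruitment): 500 × (1 − 0.20) = 400.
- Pilot rate (III): 75 / (75 + 15) = 75/90 = 83.3% (Wilson 95% interval 74% to 90%).
- Table 2, with g groups of m patients per arm: n_eff = g·m / (1 + (m − 1)·ICC), and power ≈ Φ(d·√(n_eff/2) − 1.96). For 10 groups of 20 at ICC 1%: 200/1.19 = 168.1. With d = 0.31 power is 81.1%, against 168 and 81% in the table. The other five rows also reproduce, to within rounding or one unit of effective sample size.

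So the arithmetic of the plan is right. The question is which event the 400 counts.

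**Does the 83% support 20% loss from the initial assessment?** Let c be the share of the Pre-NDPP arm that attends the pre-session. The documents do not give c. If those who miss the pre-session do not join a class (also an assumption), the start rate is c × 0.833.
- For 80% to start, c must be 0.80/0.833 = 96%.
- At c = 90%, 80% or 70% (assumed), 75%, 67% or 58% start, which is 188, 167 or 146 of 250.

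For usual care no calculation is possible, because no rate is given.

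**What if the share with 12-month weights is not 80%?** Let r be the share of 250 per arm with a weight. The documents give no value, so r is an assumed range. With 10 groups per arm, as in the 200-per-arm rows of Table 2, m = 25r. Loss is taken as equal across groups and arms, and only observed weights are counted.

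| r | Per arm | Power, 0.31 SD, ICC 1% | Power, 0.36 SD, ICC 1.44% | Detectable SD at 80% power, ICC 1.44% |
|---|---|---|---|---|
| 80% | 200 | 81% | 89% | 0.316 |
| 70% | 175 | 77% | 86% | 0.333 |
| 60% | 150 | 71% | 81% | 0.355 |
| 50% | 125 | 64% | 75% | 0.383 |

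Example, r = 60% at ICC 1%: m = 15, n_eff = 150/1.14 = 131.6, 0.31 × √65.8 = 2.51, 2.51 − 1.96 = 0.55, Φ(0.55) = 0.71.

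The pair 0.31 SD and ICC 1% is a Table 2 row. The pair 0.36 SD and ICC 1.44% is the pilot result, which Sample size and power gives for weight change in the NDPP. That section plans on about 0.28 to 0.35 for all randomised participants.

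**The case against.** The strongest reply is that follow-up for weight is separate from class attendance and is already planned for everyone. Table 1 (IV.A) schedules baseline and 12-month weights for all randomised participants, with gift cards. Retention adds the payment and the home-scale option, and IV.A allows a photograph of the scale to be sent in. This stands. Attenders are not an upper bound on weights, so a reader who infers that the trial will fall short of 400 weights goes further than the documents allow. The pilot's mean stay of 96.5 days does not help that inference: it measures time in the programme, not completion of a paid final weight.

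A reader might also infer that the 83% generated the 400. It did not. 83.3% of 500 is 417; the 400 comes from the stated 20% loss. The 83% is an example, cited beside the 2013-2017 delivery. It is the only retention number shown, and no more than that.

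Nor is the trial shown to be underpowered. Table 2 already covers 360 analysed, a 28% loss, and at the pilot effect power holds at about 81% with 60% of weights. The limit on this reply is that the plan itself expects a smaller effect in all randomised participants.

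On dropout, the plan does mention imputation and keeps people lost to follow-up in the analysis. But General quantitative approaches (IV.F) describes its missing-data methods for longitudinal analyses and contrasts these with the single-outcome primary analysis, for which no imputation method is named. Imputation would not, in general, restore all the information lost with the missing weights.

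Finally, the documents do not limit monitoring to class attenders: Table 1 tracks consent, pre-session completion, attendance and reasons for dropout. What they lack is a target for 12-month weights.

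**Conclusion.** The concern holds in a limited form. The power-based goal counts class attendance when it should count 12-month weights. The allowance for attrition in the primary analysis has no stated completion rate behind it. The 83% does not support 20% loss from the initial assessment in either arm.

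The effect on power depends on a completion rate that the documents do not give. Relative to 80% of weights, obtaining 60% costs about 10 points of power at 0.31 SD and ICC 1% (81% to 71%), and about 8 points at 0.36 SD and ICC 1.44% (89% to 81%). These figures assume 10 groups per arm, equal loss between arms and analysis of observed weights. Bias from unequal loss would be additional, and its size cannot be worked out from the documents. The point should be corrected while 12-month weights can still be collected.

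**What to change.** - In Recruitment and Retention (IV.C), keep attendance at one or more sessions as an engagement goal. Set the power-based target as a 12-month weight from at least 400 of the 500 randomised, 200 per arm, counting people who declined or left the NDPP, and track it by arm. The 400 is what the 200-per-arm rows of Table 2 require, not a forecast. The expected completion rate by arm, with its source, should be stated beside it.
- Describe the 83% as the rate among pilot pre-session attenders only.
- Reword the sentence on dropout to say that leaving the programme does not remove a participant from the primary analysis, provided the 12-month weight is obtained.
- Where the final visit is missed, use the EHR clinic weight nearest month 12 within a prespecified window, flag it, and check its influence in a sensitivity analysis.

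The cost is protocol wording, one tracking field, and EHR abstraction for missed visits. There are two downsides: EHR weights are less standardised than study weights, and the stated support for retention becomes less favourable.

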Randomization. We will randomize eligible, consenting participants to receive either the enhanced intervention (Pre-NDPP + standard NDPP) or usual care control group (standard NDPP only) in a 1:1 ratio. After defining our randomization parameters, including allocation by varying block sizes and stratification by demographic characteristics, we will use the Randomization Module of the Research Electronic Data Capture system (REDCap) to manage random assignment of participants.

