General quantitative approaches. Differences in characteristics between study groups will be assessed using chi-square and t-tests to examine potential sampling bias. Percent weight change is the primary outcome, which has a well-documented association with T2D incidence.^{2,20} ITT analyses will include all randomized participants regardless of NDPP participation, including those lost to follow up. Weight loss data for women who become pregnant during the study will be excluded from analyses. Patient-level covariates will be screened in bivariate analyses and included in multivariate analysis if related to the outcome at p<.2, differ between treatment arms, or associated with dropout. Covariates and potential moderators will include age, gender, race/ethnicity, primary language, comorbidities, and other demographic and clinical variables. Although primary analyses examine a single outcome per patient (e.g., percent weight loss), for longitudinal analyses (e.g., perceived risk) we will determine whether missingness patterns are ignorable or nonignorable. 51-54 If so, we will employ likelihood-based methods that use all available data, adjusting for covariates associated with missingness. If missingness is non-ignorable we will use pattern mixture models.⁵⁵ If normality assumptions are not met, we will use transformations to normalize distributions, ordinal or Poisson regression where appropriate, and/or the appropriate link function and distribution (e.g., logit link, gamma distribution). We will use general (generalized) linear mixed models to incorporate data structures that may be both hierarchical (patients within groups) and longitudinal (repeated observations over time). 56,57 Hypothesis tests will be two-sided with α=.05 or p values reported. Goodness of fit statistics and model fitting diagnostics will be used to assess for influential points, outliers, overdispersion, and heteroscedasticity and to evaluate alternative model specifications.⁵⁷ SAS version 9.4 (SAS Institute Inc., Cary, NC) will be used for analyses.

Aim 1: To evaluate clinical effectiveness of the Pre-NDPP intervention.

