Hypothesis 1.1. Pre-NDPP participants will experience greater weight loss than those directly enrolled into NDPP. The primary outcome for this analysis will be percent weight change among all randomized participants. As study participation includes groups of individuals in the same study arm, the data structure will be hierarchical, with patients nested within groups. Statistical models are shown in hierarchical notation below.

Likelihood of achieving ≥5% weight loss in the NDPP will also be evaluated (using generalized linear mixed models with logit link), as well as percent weight change from first to last NDPP sessions attended.

Level 1 model. Individual outcomes will be modeled as a function of patient characteristics (fixed effects), such as sociodemographic variables, baseline BMI, and comorbid conditions: $Y_{ij} = \beta_{0j} + \beta_{1j} X_{1ij} + \beta_{2j} X_{2ij} + ... + \beta_{pj} X_{pij}$ Level 2 model. Group level models specify relationships between group-level predictors and coefficients in the Level 1 model. The intervention effect is included as 0 if control, 1 if intervention: $\beta_{0j} = \gamma_{00} + \gamma_{01}$ (intervention)+ u_{0j} . Thus, for a standardized model, γ_{00} is adjusted mean weight loss for patients in the standard condition (i.e., no pre-session intervention), γ_{01} represents the average increment (decrement) from the mean for groups with intervention patients, and u_{0j} is a group level random effect that reflects between-group variance and is the difference between group means and the predicted mean based on the model, and $u_{0j} \sim N(0,\tau_{00})$. Thus, Hypothesis 1.1 can be tested as H_0 : γ_{01} =0 vs H_1 : γ_{01} ≠0.

Hypothesis 1.2. Pre-NDPP participants will have greater engagement in the NDPP than those who are directly enrolled into the program. The outcome variables, number of sessions attended and days of participation, will be analyzed using similar approaches. If the distribution of outcomes is non-normal we will use generalized linear mixed models with the appropriate distribution and link function, as described above. We will also examine the dichotomous outcome of ≥1 NDPP session attended using multilevel logistic regression (generalized linear mixed model with logit link and random effect for group).

Aim 2: To examine mediators and moderators of Pre-NDPP outcomes.

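### Primary-model covariates are picked by screening the trial data and the stratification factors are not required, so the primary model is not prespecified and need not reflect the randomization

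*Combined protocol and SAP*

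**What the plan says.** Section IV.C, Randomization, allocates 1:1 through REDCap, "including allocation by varying block sizes and stratification by demographic characteristics". The factors are not named there or anywhere else.

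Section IV.F, General quantitative approaches, begins with a baseline comparison of the arms: "Differences in characteristics between study groups will be assessed using chi-square and t-tests to examine potential sampling bias". Covariates are then screened one at a time and "included in multivariate analysis if related to the outcome at p<.2, differ between treatment arms, or associated with dropout". Only the outcome route has a threshold; what counts as differing between arms, or as associated with dropout, is undefined. The candidates are open-ended: "Covariates and potential moderators will include age, gender, race/ethnicity, primary language, comorbidities, and other demographic and clinical variables". The same paragraph allows fit statistics and diagnostics to be used in weighing other specifications.

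Section IV.F, Hypothesis 1.1, gives the primary model. At level 1, "Individual outcomes will be modeled as a function of patient characteristics (fixed effects), such as sociodemographic variables, baseline BMI, and comorbid conditions". At level 2, "The intervention effect is included as 0 if control, 1 if intervention", with a random effect for class, and the primary test is of γ01 = 0.

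No section fixes a covariate set, puts the stratification factors in the model, or names an unadjusted or strata-only analysis as primary.

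**The concern.** The usual principle is that the primary analysis reflects the randomization: factors used to stratify allocation are in the model whether or not they look prognostic in the data at hand. Here a stratification factor must pass a screen like any other variable. Two of the three entry routes have no cut-off and the candidate list has no end, so two analysts who both follow the text could fit different models and report different primary estimates and p values. Selection on arm difference is also poorly founded, because after randomization such differences are due to chance and are not evidence of sampling bias.

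This trial is meant to confirm a non-randomized pilot. What is at stake is a primary result that can be reproduced from the plan.

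**Working it through.** **1. The plan's own figures.** Section IV.F, Table 2, uses an unadjusted formula: effective sample size per arm = (groups × m) / (1 + (m − 1) × ICC), where m is patients per group. For example, 180/1.17 = 153.8 and 200/1.38 = 144.9. The six rows give 153.8, 134.3, 168.1, 144.9, 201.7 and 173.9 (stated: 154, 134, 168, 145, 201, 174), with power of 80.1, 81.8, 81.1, 80.2, 80.3 and 82.4% (stated: 80, 82, 81, 80, 80, 82). Table 2 reproduces, and the present point does not change it.

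**2. How a stratification factor can enter.** Stratified blocks balance the factor by design, so the arm-difference route will rarely admit it. That leaves the outcome screen and an undefined association with dropout.

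**3. Chance of failing the outcome screen, and its cost.** Inputs: n = 500 randomized, or 400 after the 20% early attrition in Section IV.C. The share of outcome variance explained by the factor (R²) is assumed, because the documents give none.

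- ncp = √(n·R²/(1 − R²))
- P(fail) = Φ(1.28 − ncp) − Φ(−1.28 − ncp)
- Patient-equivalents lost if omitted = n·R²/(1 − R²)
- Expected loss = P(fail) × patient-equivalents lost if omitted

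| R² | P(fail), n = 500 / 400 | Lost if omitted | Expected loss |
|---|---|---|---|
| 0.5% | 38% / 44% | 2.5 / 2.0 | 0.95 / 0.89 |
| 1% | 17% / 23% | 5.1 / 4.0 | 0.84 / 0.94 |
| 2% | 2.8% / 5.8% | 10.2 / 8.2 | 0.28 / 0.47 |
| 5% | 0.006% / 0.05% | 26.3 / 21.1 | 0.002 / 0.01 |

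P(fail) is an upper bound on omission, because a factor that fails here may still enter by another route.

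**4. Simulation of the whole rule.** Set-up: 4,000 replicates per scenario, N = 500, blocks of 4 and 6 within four strata formed by two binary factors, and eight further candidates, three of them prognostic except in the 0% scenario. The assumed cut-offs were p<.05 for arm difference and p<.05 for association with a random 20% dropout indicator. Class clustering was not simulated. Monte Carlo error is about 0.35 points.

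| Variance explained by strata | Both strata selected | Type I error: rule | Rule + forced strata | Unadjusted |
|---|---|---|---|---|
| 0% | 5.5% | 4.7% | 4.7% | 4.5% |
| 2% | 70.8% | 5.5% | 5.5% | 5.3% |
| 5% | 97.8% | 4.9% | 5.0% | 4.2% |
| 10% | 99.98% | 4.6% | 4.6% | 3.7% |
| 20% | 100% | 4.3% | 4.3% | 2.3% |

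The rule selected 54 to 660 distinct models across replicates, depending on the scenario. At a standardized effect of 0.28, with strata explaining 5% and 10%, power was 91.9% and 92.9% under the rule, the same with strata forced in, and 87.9% and 89.2% unadjusted.

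**5. Adjusting versus not adjusting, with clustering.** If covariates explain within-class variance only, SE ratio = √((DE − R²)/DE), with DE = 1 + (m − 1) × ICC. Across Table 2, DE runs from 1.17 (m = 18, ICC 1%) to 1.38 (m = 20, ICC 2%).

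- R² = 5%: √(1.12/1.17) = 0.978 and √(1.33/1.38) = 0.982, a cut of 1.8 to 2.2%.
- R² = 10%: √(1.07/1.17) = 0.956 and √(1.28/1.38) = 0.963, a cut of 3.7 to 4.4%.

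**The case against.** The strongest reply is that the rule does almost no damage. Type I error and power are essentially the same with and without forced strata. A strong stratification factor is nearly always selected, and the one omitted in 94.5% of replicates explains nothing, so its omission costs nothing. This stands, and it rules out two stronger readings.

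- A reader might infer that letting the outcome choose the covariates inflates type I error. Applied mechanically, it did not. Reporting the smallest p among four models (unadjusted, strata, screened, all covariates) gave 5.3 to 6.7%, but the plan does not propose that. It only fails to exclude it.
- A reader might infer a loss of about 26 patients (500 × 0.05/0.95) or 56 (500 × 0.10/0.90). Those figures compare adjusting with not adjusting, ignoring clustering. The rule does adjust for factors that strong, so they are not its cost.

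A second reply is that the variables named in Section IV.F and Hypothesis 1.1 form a fixed set that would cover any demographic stratum. This does not stand. The Section IV.F list directly follows the screening sentence, is shared with moderators and is open-ended; the Hypothesis 1.1 list is only illustrative. Neither can be matched to unnamed strata. Income, a demographic variable in Section IV.A and a moderator in Aim 2, is not named in either list.

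A third reply is that the dropout route does useful work. This stands. Section IV.C, Retention, refers to the analysis plan for imputation, but the missing-data methods there are written for the longitudinal analyses. Conditioning on predictors of dropout is the only protection described for the single-outcome primary analysis, so it should not be removed without a replacement.

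**Conclusion.** The point holds as one of prespecification. The primary model is chosen from the trial data, and the factors that governed allocation can be left out of it. The demonstrated numerical effect is small: type I error of about 5%, and an expected loss of under about 1 patient-equivalent per weak factor with R² of 0.5 to 1%. These sizes rest on assumed R² values, assumed cut-offs for the two undefined routes, two assumed binary strata and a simulation without class clustering.

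It is still worth correcting. The plan states a selection rule where it could state a model, and the change is inexpensive.

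**What to change.** - Name the stratification factors in Sections IV.C and IV.F.
- Before outcome data are seen, fix the primary model as arm + stratification factors + baseline weight or BMI + a short prespecified set from variables the plan already names (for example age, gender, race/ethnicity, language and income), with the class random effect. The exact set matters less than that it is fixed and contains the strata.
- Drop the p<.2 and arm-difference rules for the primary analysis, and keep the screened model as a sensitivity analysis.
- Keep prespecified baseline predictors of dropout in the primary model. Move them to an imputation model only if one is specified for the primary outcome.

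The cost is wording. Demographics and baseline weight and BMI are already collected, and visits, sample size and Table 2 are unchanged. Writing an imputation model would be additional work, needed only if that option is taken.
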